We will perform sparse sampling pre-dose and at 1, 2.5, 4, 6 and 8 hours after TB drug dosing at day 3 of TB treatment and store plasma at -80°C. Isoniazid, rifampicin and pyrazinamide concentrations will be measured using LC-MS. The PK measurements will be performed on stored, batched samples and thus results of these assays will not be available in real-time and thus will not influence patients management. The UCT Clinical Pharmacology Laboratory has performed many TB drug PK studies [69, 73-75]. Population PK modelling will be used to predict important PK parameters (C_{max} and AUC). Findings would inform further research to optimize initial dosing or route of administration (eg. intravenous) of TB medication in severe HIV-TB.

Methodology:

Study design:

Prospective cohort study of 660 HIV-TB inpatients.

Sample size calculations:

The primary outcome was dichotomised (survivors vs fatal outcome). The calculations have been performed for major experiments relating to urinary LAM concentration, plasma LPS concentration and proportion with detectable CMV viraemia. Cumulative mortality of 15% has been factored: lower than reported (9). We assume in a prospective study with ART initiation at 2-8 weeks mortality will be lower than reported from routine settings.

Urinary LAM concentration (ng/ml). Mean level of urinary LAM of 1.62 ng/ml in survivors has been estimated based on HIV-TB outpatient data obtained from author of [76], [name]:

Survivors Urinary LAM (Mean; SD)	Fatal outcome Urinary LAM (Mean; SD)	Fold change	Alpha	Beta	Sample size
1.62; 3.2	2.43; 3.2	1.5	0.05	0.2	962
1.62; 3.2	3.24; 3.2	2	0.05	0.2	242
1.62; 3.2	4.05; 3.2	2.5	0.05	0.2	108

Plasma LPS concentration (pg/ml). Mean level of LPS in survivors of 128 pg/ml estimated, based on [17]:

Survivors Plasma LPS (Mean; SD)	Fatal outcome Plasma LPS (Mean; SD)	Difference %	Alpha	Beta	Sample size
128, 56	160, 56	25	0.05	0.2	160
128, 56	154, 56	20	0.05	0.2	286
128, 56	147, 56	15	0.05	0.2	536

Detectable CMV viral load by PCR (> 150 copies/ml). Based on [48] it was estimated that CMV viraemia would be detectable in 10-20% survivors (higher than in [48] because participants will have more advanced HIV):

Survivors % CMV viral load detectable	Fatal outcome % CMV viral load detectable	Alpha	Beta	Sample size
20%	40%	0.05	0.2	334
20%	30%	0.05	0.2	1178
10%	30%	0.05	0.2	246
10%	20%	0.05	0.2	786

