660 patients will be enrolled. Assuming 5% loss to follow up, 630 patients will complete the study. We will exclude from major analyses patients diagnosed with rifampicin resistance (estimated 5% [77], n=30), leaving 600 for analysis. This will allow us to detect statistical significance for a two-fold difference in urinary LAM, a 15% difference in plasma LPS and a difference in the percentage of patients with detectable CMV viraemia of 20% in survivors and 40% in those with fatal outcome (or 10% and 30% respectively).

Sample size for FACS experiments (44 fatal cases vs 246 survivors) was based on Annexin-V experiments, allowing us to detect a significant difference in the proportion of CD4 T-lymphocytes that are Annexin-V+ of 5% in survivors and 20% in those who die (alpha=0.05, beta=0.2).

Characteristics of the study population:

Number of participants:

660 participants with HIV-TB co-infection.

Inclusion criteria:

1. Microbiological diagnosis of TB, or clinical diagnosis that fulfills WHO criteria for smear-negative or extrapulmonary TB [78] or suspected to have active TB based on clinical presentation
2. 18 years or older
3. Informed consent from patient (unless drowsy/confused – see below)
4. HIV seropositive
5. CD4 count \leq 350cells/ μ l

Exclusion criteria:

1. HIV seronegative or testing declined
2. Pregnant
3. 3 or more doses of TB treatment received during the admission or has been on TB treatment within one month of admission

TB case definitions:

TB will be investigated with 2 sputa for Xpert MTB/RIF and TB culture, Myco/F Lytic blood culture, urinary lipoarabinomannan (LAM) and samples from appropriate extrapulmonary sites for TB culture. Chest radiographs will be performed in all and abdominal ultrasound at clinician discretion. We will stratify analyses according to:

- 1) Confirmed TB: Microbiologically proven TB (by culture or Xpert MTB/RIF, or post-mortem findings of AFB+ or culture+) (predicted to be > 70% based on previous study at our hospital [79])
- 2) Probable TB: TB not confirmed, but urinary LAM+ or fulfill WHO criteria [78] unless an alternate diagnosis is made during follow-up or post-mortem.

Vulnerability:

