Data quality control and assurance measures will be put in place. These will include having all clinical data capture forms being checked and signed off by one other member of the study team. Data entered on the study database will be entered by one data capturer, but will be checked by a member of the study team or by another data capturer. Any errors will be recorded and discussed at the monthly study meeting. Upon completion of the study we will ensure that 3 copies of the raw data are backed-up for long term storage: one on a UCT server, one on a remote server and one on an external hard-drive that the applicant will keep secure. These data capture, entry, management and access systems have been developed in the course of many TB-HIV and other HIV studies that we have undertaken to date.

Data analysis:

TB suspects who do not have active TB (after full clinical investigation has been completed and all results obtained) will not be included in the analysis of primary endpoints. Their data may be used in secondary analyses or as control subjects. Univariate analysis will compare those who survive 12 weeks to those with fatal outcome. Bonferroni correction for multiple comparisons will be performed where appropriate. Multivariable logistic regression modeling will be approached based on pre-specified hypotheses, articulated where possible through directed acyclic graphs. Demographic variables, CD4 count, viral load, antibiotic treatment will be explored as potential confounders in addition to hypothesis specific variables. Comparison with non-TB control patients will be performed for several of the experiments as described. Data will be analyzed using de-identified study numbers.

Description of risks and benefits:

Potential risks and discomforts: This is an observational trial and there are no study specific interventions. Collection of study samples by means of phlebotomy carries minimal risk of bruising, infection at the collection site and bleeding after phlebotomy. Phlebotomy may be uncomfortable or painful during the procedure, but this resolves as soon as the procedure has been completed. The total volume of blood drawn is ~ 55ml. This amount of blood drawn would not cause complications unless patients are severely anaemic.

Risk classification: The study as a whole carries minimal risk for participants and harm due to study participation is not anticipated.

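### The figure of 600 analysable patients makes no allowance for TB suspects later found not to have TB, so 80% power for the 15% LPS difference is not assured

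*Protocol*

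**What the plan says.** All references are to the Protocol.

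- **Attrition (Sample size calculations).** "660 patients will be enrolled. Assuming 5% loss to follow up, 630 patients will complete the study". A further 30 patients, an estimated 5%, are removed for rifampicin resistance, "leaving 600 for analysis". No other deduction is made.
- **Claim (same section).** "This will allow us to detect statistical significance for a two-fold difference in urinary LAM, a 15% difference in plasma LPS", together with CMV viraemia of 20% against 40%, or 10% against 30%.
- **LPS table.** The survivor mean is 128 pg/ml, the SD 56, alpha 0.05 and beta 0.2. Fatal-group means of 160, 154 and 147 (differences of 25, 20 and 15%) are given totals of 160, 286 and 536. Mortality of 15% is assumed throughout.
- **Inclusion criteria.** The first criterion accepts a microbiological diagnosis, a clinical diagnosis meeting WHO criteria, "or suspected to have active TB based on clinical presentation".
- **Data analysis, exclusions.** On who enters the primary-endpoint comparison, the rule is: "TB suspects who do not have active TB (after full clinical investigation has been completed and all results obtained) will not be included".
- **Data analysis, multiplicity.** "Bonferroni correction for multiple comparisons will be performed where appropriate". No family of comparisons is named. LAM, LPS and CMV are each sized at alpha 0.05.

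**The concern.** Excluding suspects who turn out not to have TB reduces the primary analysis set in the same way as excluding rifampicin resistance. One is deducted and the other is not. The 660 is stated as the number enrolled, and the protocol does not say that excluded suspects will be replaced. The analysable number must therefore be below 600 unless every suspect is confirmed or classed as having TB.

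Whether this matters depends on the reserve behind each claim. LPS needs 536 of the 600, far more than LAM (242) or CMV (334 or 246). LPS is thus the claim most exposed to the missing deduction, and to any gap between the alpha used for sizing and the alpha used for testing. At stake is how a null LPS result is read: the text invites the reader to treat a 15% difference as ruled out with at least 80% power.

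**Working it through.** **Inputs.** SD 56, survivor mean 128 and fatal-group mean 147 (difference 19 pg/ml) from the LPS table; 15% mortality, alpha 0.05 and beta 0.2 from Sample size calculations. Sidedness is not stated. Two-sided testing reproduces the table (one-sided gives about 421 for the 15% row).

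**Formula.** Total N = (z_alpha + z_beta)² × SD² × (1/0.15 + 1/0.85) / d², where 1/0.15 + 1/0.85 = 7.843.

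**Reproducing the plan's figures** (alpha 0.05: (1.960 + 0.842)² = 7.849, so N = 193,052/d² for LPS):

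| LPS row | d | Computed N | Stated N |
|---|---|---|---|
| 15% | 19 | 534.8 | 536 |
| 20% | 26 | 285.6 | 286 |
| 25% | 32 | 188.5 | 160 |

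The same formula gives 961, 240 and 107 for LAM (stated 962, 242, 108). With a continuity correction, the four CMV rows come to about 333, 1176, 245 and 785 (stated 334, 1178, 246, 786). The method is therefore identified, and only the 25% LPS row fails. With 160 patients that row has 73% power: 32 / (56 × √(7.843/160)) = 2.581, and 2.581 − 1.960 = 0.621.

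**Power of the 15% LPS claim as stated.** At N = 600 the standard error is 56 × √(7.843/600) = 6.403. Then 19/6.403 = 2.967, less 1.960 leaves 1.007, so power is 84.3%. The reserve is 600 − 536 = 64 patients, or 10.7% of the 600 (10.9% using 534.8).

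**Effect of the two rules.** The protocol gives no non-TB share, so the shares below are assumptions, taken as percentages of the 600. Bonferroni is shown for families of two and three because the protocol names none.

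| Non-TB share (assumed) | N | Power, alpha 0.05 | Power, alpha 0.025 | Power, alpha 0.0167 |
|---|---|---|---|---|
| 0% | 600 | 84% | 77% | 72% |
| 10% | 540 | 80% | 72% | 66% |
| 20% | 480 | 76% | 66% | 60% |
| 30% | 420 | 70% | 60% | 54% |

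For 80% power the analysable N would have to be about 648 at alpha 0.025 and 714 at alpha 0.0167.

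**LPS difference detectable with 80% power** (as % of 128 pg/ml):

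| N | alpha 0.05 | alpha 0.0167 |
|---|---|---|
| 600 | 17.9 pg/ml, 14% | 20.7 pg/ml, 16% |
| 540 | 18.9, 15% | 21.8, 17% |
| 480 | 20.1, 16% | 23.2, 18% |
| 420 | 21.4, 17% | 24.8, 19% |

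**The other claims.** At alpha 0.0167 the required totals are about 321 for the two-fold LAM difference, 428 for CMV 20% against 40% and 309 for CMV 10% against 30%. All are met at N = 480. At the extreme corner (N = 420 and alpha 0.0167) only CMV 20% against 40% falls short, by about 8 patients.

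**The case against.** The strongest reply is that the sentence is right on its own inputs: 536 reproduces, and 600 patients at alpha 0.05 give 84% power. A reader might infer that the protocol's own rules mean the stated power is not delivered. The documents do not support that flat statement, for three reasons.

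- **Bonferroni is conditional.** It applies where appropriate, and nothing places LAM, LPS and CMV in one family. They belong to separate aims (1a, 1b, 1c), and many other markers are compared as well. A family of three is an illustration, and defining the family is commonly left to a statistical analysis plan. What stands is narrower: any Bonferroni correction that covers LPS, even over two comparisons, takes power below 80%, and the sizing does not allow for it.
- **The non-TB share is unknown.** At alpha 0.05 about 10% can be absorbed. Only part of the cohort enters as suspects, so a given failure rate among suspects removes a smaller share of the 600. The 30% end also fits poorly with TB case definitions, which predicts more than 70% confirmed TB with probable TB on top, if that figure refers to enrolled patients.
- **660 might mean patients with TB.** The protocol describes the 660 as HIV-TB patients. But it also states 660 as the number enrolled, under criteria that admit suspects, so the two statements need reconciling.

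A reader might also infer that LPS determined the size of the study. No section says so; 536 is only the largest requirement among the claims made. The 25% LPS row is a genuine slip, but no claim rests on it.

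**Conclusion.** The point holds in a limited form. The 600 is overstated because a planned exclusion from the primary analyses is missing from the attrition line. This needs no outside figure, although its size does.

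For the 15% LPS difference, 80% power is not assured. It is kept if no more than about 11% of the 600 prove not to have TB and LPS is tested at 0.05. It is lost if either condition fails: 76% power at an assumed 20% non-TB share, 77% with Bonferroni over two comparisons at N = 600, 72% over three. These figures rest on the protocol's SD of 56, 15% mortality and two-sided testing.

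The LAM and CMV claims survive, apart from the marginal shortfall for CMV 20% against 40% when the most severe assumptions are combined. The documents do not show that the study is underpowered as a whole or needs more patients. The error in the 25% LPS row is certain but minor.

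**What to change.** Change the text of Sample size calculations; no extra enrolment is needed.

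1. Add an expected share of enrolled patients found not to have TB to the attrition line, with its source, and replace 600 with the resulting number.
2. State whether the Bonferroni rule covers LAM, LPS and CMV, and use the same alpha for sizing as for testing.
3. Restate the LPS difference detectable with 80% power to match: about 14 to 17% at alpha 0.05, or 16 to 19% at alpha 0.0167, for 600 down to 420 analysable patients.
4. Correct the 25% LPS row (128 against 160, SD 56) from 160 to about 190.

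The cost is a wording amendment and, in most of these cases, a somewhat less favourable LPS statement.

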Relatives will be approached for permission for post-mortem examinations. If unwilling to have a full post-mortem performed, permission will be sought to undertake post-mortem needle biopsies of lung, liver and spleen and bone marrow – an approach that yields important diagnostic information in HIV-infected patients [14, 81]. Tests performed on tissue samples will include: histological stains; Gram, fungal and ZN stains; immunohistochemical staining (CMV); and bacterial, TB and fungal cultures. This study will be performed in collaboration with [name] (Anatomical Pathology, UCT).

Study Outline of Activities:

	D0	D3	Wk2	Wk4	Wk8	Wk12	Deterioration
Informed consent	x						
Clinical Assessment	x	x				x	x
Samples Collected	x	* PK					#x
^Δ ART initiation CD4 ≤ 50			x				
^Δ ART initiation CD4 >50			x				

D: Day

Wk: Week

ART: Antiretroviral Therapy

PK: PK substudy in a subset of participants

* PK samples will be stored and run in batches retrospectively.

Samples taken at time of deterioration will not be research samples, but standard of care samples appropriate to investigate the patients' condition at that time point.

^Δ If patient is not on ART at time of recruitment

Detailed Study Procedures:

Study procedure	Time Point	Detail	Volume	Standard of care or research
Clinical Assessment	All time points	Examine for features of sepsis syndrome and TB IRIS	NA	Standard of care
	D0	* Pan ophthalmic fundoscopy for features of CMV retinitis	NA	Research
Echocardiography	D0 & Deterioration	* Assess left ventricular function	NA	Research
Blood tests	D0 & Deterioration	Chemistry: * Glucose	2 ml	Standard of care
		* Lactate		Research
		* D-dimer	5 ml	Research
		* Pro-calcitonin	1 ml	Research
		* Venous blood gas	1 ml	Research
		* Liver function tests	5 ml	Standard of care
		* Renal function tests		Standard of care
		* CRP		Standard of care
		Haematology: * Full blood count and differential	4 ml	Standard of care
		Plasma: LPS concentration	2 ml	Research
		Soluble CD14	1 ml	Research
		Intestinal fatty acid binding protein	1 ml	Research
		Microbiology: * Bacterial blood culture	8 ml	Standard of care
		* Mycobacterial blood culture	5 ml	Research
		* Serum cryptococcal antigen lateral flow assay	0.5 ml	Research
		Virology: CMV viral load	2 ml	Research
		* HIV viral load	2 ml	Research
		Immunology: PBMC	10 ml	Research
		* CD 4 count	2 ml	Standard of care
		Genetic: DNA	2 ml	Research
Luminex and ELISA for cytokines	Plasma from PBMC sample	Research		

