PLEX-ID assay for bacterial DNA	3ml	Research		
Urine	D0 & Deterioration	Urinary LAM assays	20 ml	Research
Sputum	D0 & Deterioration	* Gene Xpert MTB/RIF and TB culture	NA	Standard of Care
Chest Xray	D0 & Deterioration	* Evaluate for any abnormality	NA	Standard of care
Sputum bacterial cultures	D0 & Deterioration	* All patients with infiltrate on CXR	NA	Research
Bacterial cultures on other samples	D0 & Deterioration	* Pus, urine or other samples as appropriate	NA	Standard of care
Post mortem examination	Death	If family consents to post mortem	NA	Research

D: Day

Wk: Week

NA: Not applicable

* These tests will be performed in real time and results will be made available to managing doctors as soon as the lab result is available.

Note: If any of these samples have been taken by hospital staff within 2 days of enrollment they will not be repeated but the results from the hospital sample will be used.

Consent will specifically be taken from patients for storage of remaining plasma, serum, urine and PBMC for potential future substudies (such substudies would require specific HREC permission). In addition, we will store a sample of DNA for potential future studies of genetic polymorphisms associated with outcome in HIV-TB. Again consent will be specifically obtained for this with a separate Genetic ICF. It will be made clear to participants that sample storage is optional.

In addition, PK samples will be performed on a subset of participants as described above on day 3 of TB treatment with 4ml of blood drawn at each of the timepoints (pre-dose, 1, 2.5, 4, 6 and 8 hours after taking TB medication). Samples for PK studies will be stored and run in batches and will thus not be performed in real time. Results will not be available to attending medical teams.

Control cohort of non-TB HIV-infected patients:

We will enroll a cohort of 90 hospitalised ART-naïve HIV-infected patients with CD4 counts $\leq 350/\mu\text{l}$. We will exclude TB (2 sputum cultures and urinary LAM all negative). These will be patients admitted with other HIV-related conditions (eg. cryptococcal meningitis, pneumocystis pneumonia, Kaposi's sarcoma).

Data collection methods:

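### The protocol contradicts itself on research sampling at deterioration, and its stated blood total of about 55 ml covers one D0 draw only

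*Protocol*

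**What the plan says.** **Outline table.** In Study Outline of Activities, the row for samples has entries at D0, at D3 (PK subset) and at deterioration. The footnote to the deterioration entry reads: "Samples taken at time of deterioration will not be research samples, but standard of care samples".

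**Detailed table.** In Detailed Study Procedures, the blood-test block carries the time point "D0 & Deterioration". Its rows labelled Research include D-dimer, procalcitonin, LPS, sCD14, I-FABP, mycobacterial culture, CMV viral load and PBMC. The same time point appears in separate rows, also labelled Research, for echocardiography, urine ("Urinary LAM assays") and sputum bacterial culture ("All patients with infiltrate on CXR"). Fundoscopy is listed at D0 only.

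**Blood volume.** Description of risks and benefits states: "The total volume of blood drawn is ~ 55ml". The PK text after the detailed table adds "4ml of blood drawn at each of the timepoints", with six time points. Minimizing risk limits the volume to 30 ml in symptomatic anaemia (haemoglobin below 8 g/dl with attributable symptoms). It does not say whether that is per draw or overall.

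**Where minimal risk is used.** The risk section classes the whole study as minimal risk. The Vulnerability section relies on minimal risk when it asks to enrol confused or drowsy patients who cannot consent, and asks for this specifically for the naso-gastric PK group.

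**The concern.** The footnote and the table give opposite instructions for the same event, so staff must choose whether to draw research blood, urine and sputum from a patient who has just become worse.

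Two things depend on the choice. The first is the blood volume given to the ethics committee. It is called a total, but appears to describe one draw, and it supports a minimal-risk classification in a population that is often anaemic: in Appendix 3 the median haemoglobin was 9.0 g/dl in survivors and 7.6 g/dl in those who died.

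The second is the marker analysis. Sections 1a and 1b compare markers between fatal cases and survivors without naming the sample used. If research samples at deterioration were taken and used in that comparison, the time of sampling could depend on outcome, and a late value could be read as a baseline predictor.

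**Working it through.** **1. Is the contradiction an artefact of a merged table cell?** The blood block has one time-point entry for many rows, so it could be. Urinary LAM and sputum bacterial culture, however, each have their own row, time point and Research label, and both are samples. They conflict with the footnote whatever the layout of the blood block. Echocardiography has its own row too, but it is an examination, so the footnote on samples does not strictly reach it.

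**2. Reproducing the stated volume.** Inputs are the volumes in the detailed table. Shared tubes are counted once, and the cytokine assays add nothing because they use plasma from the PBMC sample.

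- Standard of care: glucose/lactate tube 2 + liver, renal and CRP 5 + full blood count 4 + bacterial culture 8 + CD4 2 = 21 ml. The first tube also serves lactate, which is labelled Research.
- Research: D-dimer 5 + procalcitonin 1 + venous gas 1 + LPS 2 + sCD14 1 + I-FABP 1 + mycobacterial culture 5 + cryptococcal antigen 0.5 + CMV 2 + HIV viral load 2 + PBMC 10 + DNA 2 + PLEX-ID 3 = 35.5 ml.
- One D0 draw: 21 + 35.5 = 56.5 ml, or 54.5 ml without the optional DNA tube.

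The stated figure of about 55 ml is therefore reproduced as a single D0 draw (1.5/55 = 2.7% difference).

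**3. Adding PK.** 6 × 4 = 24 ml, and 56.5 + 24 = 80.5 ml. Section 2 plans PK sampling in 40 + 40 = 80 cohort participants. This total holds under the footnote and under the table.

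**4. Adding one deterioration panel, if the table governs.** The lower figure draws DNA once only.

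| Draws | Total | Relative to 55 ml |
|---|---|---|
| D0 | 56.5 ml | 1.03 |
| D0 + PK | 80.5 ml | 1.46 |
| D0 + one deterioration | 56.5 + 54.5 = 111 to 56.5 + 56.5 = 113 ml | 2.02 to 2.05 |
| D0 + PK + one deterioration | 135 to 137 ml | 2.45 to 2.49 |

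Research blood alone, for D0 and one deterioration without PK: 35.5 + 33.5 = 69 ml to 35.5 + 35.5 = 71 ml.

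If the footnote governs, study blood outside the PK subset stays at one D0 draw, and about 55 ml stands.

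**5. The 30 ml limit.** In one draw, 30 − 21 = 9 ml remains for research tubes. If the limit is a total and an affected patient is in the PK subset, the standard-of-care tubes and PK draws alone make 21 + 24 = 45 ml. Its scope therefore matters, and it is not stated.

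**6. Which sample enters the comparison.** Section 1b plans 270 PLEX-ID assays = 90 + 90 + 90, one per person. Section 1d plans flow cytometry in 290 = 44 + 246 patients, again one per person. For LPS, sCD14 and I-FABP the protocol says all 660 participants, without giving the number or timing of samples. No passage assigns deterioration values to the comparison of fatal cases with survivors.

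**The case against.** The strongest reply is that this is a conflict between a footnote and a table, and that little follows from it.

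- **The volume is right for D0.** This stands. A reader might infer that about 55 ml is simply wrong, but the table reproduces it for a single D0 draw. It fails only as a total.
- **PK is a subset with its own consent form.** True, and that form may state its own volume, which cannot be seen here. The protocol's risk section still gives one total for a study it classes as a whole.
- **The larger totals include standard-of-care blood, and hospital samples taken within 2 days of enrolment are not repeated.** Both points are fair, so the totals are upper figures. But 35.5 ml of research blood does not reproduce 55 ml and 56.5 ml does, so the protocol's own figure counts standard-of-care tubes.
- **Outcome-dependent marker timing is conjecture.** A reader might infer that timing would differ by outcome. The document does not support that: the assay counts that are given point to one sample per person, and no cited figure shows that deterioration is concentrated in those who later die. Section 9's equivalent for TB-IRIS, in section 1e, gives a case fatality of 3.2%, which points the other way for that cause. Choosing the analysis sample is also commonly left to an SAP. What remains is conditional: timing could depend on outcome if such samples were taken and used.
- **Under the footnote, sepsis and translocation would still be assessed at deterioration.** This stands. A reader might infer that no such markers would exist, but CRP, full blood count, liver and renal function, glucose and bacterial blood culture are all labelled standard of care, and clinical sepsis assessment is at all time points.

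**Conclusion.** The contradiction is real and lies in current text. It does not depend on how the blood block is laid out, and the two passages must be reconciled. The document does not show which rule was intended.

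The stated total is accurate for one D0 draw. It is too low by the 24 ml PK component for the 80 cohort PK participants under either rule (80.5 ml). If the table governs, it is about half the true figure for anyone with one deterioration episode (111–113 ml). These sums assume that every listed tube is drawn at its listed volume, that shared tubes are drawn once, and that no tube is replaced by a recent hospital sample.

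This matters because minimal risk supports enrolment without consent, including in the naso-gastric PK group. The effect on the marker comparison is a possibility to close off, not a demonstrated bias.

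**What to change.** 1. Make the outline footnote and the detailed table state one rule for samples at deterioration. The sponsor must decide which.
2. In the risk section, replace the single total with the volume for D0 alone, for D0 with PK and, if research samples at deterioration are kept, for D0 with a deterioration panel, with and without PK. Say whether standard-of-care tubes are counted and whether the DNA tube is drawn once.
3. Reconcile the 30 ml anaemia limit with these draws by saying whether it applies per draw or across D0, PK and deterioration.
4. If research samples at deterioration are kept, state that marker comparisons between fatal cases and survivors use the D0 sample.

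The cost is wording in the protocol and, where the volume is quoted, in the consent documents. No sample size or assay count needs to change. The stated blood volume becomes less favourable for PK participants and, under the table's rule, for those who deteriorate.
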